5.3.2 Multiple Measurements within Visit Windows

If more than one assessment falls within a given window then the assessment closest to the target study day will be selected for the by-visit summaries. If two assessments are equidistant from the target day then the chronologically last assessment will be used for summary. Exceptions may be made for incomplete assessments, in which case, more complete assessments may be given priority. Details are provided in a separate programming conventions document.

For safety summaries where the most extreme values should be selected, e.g. overall post-Baseline minimum, overall post-Baseline maximum and potentially clinically important values for overall post-Baseline summaries, all non-missing post-Baseline values should be considered, regardless of whether the value is selected for the by-visit summaries. All results will be presented in data listings.

5.4 Handling of Missing Date

5.4.1 Missing or Incomplete Date for Last Dose of Study Drug

In the Safety Analysis Set, if the last dose date of study drug is missing for a subject who completed or early terminated from the study, then the date of the end-of-study/early termination visit will be used in the calculation of treatment duration. For the incomplete last dose date of the study drug, the imputation algorithms will be detailed in the analysis dataset specification document. The missing or incomplete dates will be displayed in the data listings as reported on the eCRF rather than the imputed dates.

For the data summarization before final database lock, if a subject is still ongoing, then this subject's last dose date will be imputed using the database extract date.

5.4.2 Missing or Incomplete Dates for Prior or Concomitant Medications

Missing or incomplete medication start or end dates will be imputed for the purpose of determining whether the medications are taken concomitantly (see [Section 11](#) for definition). When the chronological order of a medication's utilization relative to the study drug treatment period is unclear due to missing or incomplete date(s), the medication will be considered as concomitant. The imputation algorithms will be detailed in the analysis dataset specification document. The missing or incomplete dates will be displayed in the data listings as reported on the eCRF rather than the imputed dates.

5.4.3 Missing or Incomplete Dates for Adverse Events

Missing or incomplete adverse event (AE) start dates will be imputed for the purpose of determining whether the AEs are treatment emergent (see [Section 14.1](#) for definition). When the chronological order of an AE onset relative to the study drug treatment period is unclear due to missing or incomplete date(s), the AE will be considered as treatment-emergent. The imputation algorithms will be detailed in the analysis dataset specification document. The missing or incomplete dates will be displayed in the data listings as reported on the eCRF rather than the imputed dates.

5.4.4 Missing Severity Assessment for Adverse Events

If the severity is missing for a TEAE, then a severity of "Severe" will be assigned. The imputed values for severity assessment will be used for incidence summaries, while the actual values will be presented in data listings.

5.4.5 Missing Relationship to Study Drug for Adverse Events

If the relationship to study drug is missing for a TEAE, then a causality of "Related" will be assigned. The imputed values for relationship to study drug will be used for incidence summaries, while the actual values will be presented in data listings.

5.4.6 Character Values of Clinical Laboratory Variables

If the reported value of a clinical laboratory variable cannot be used in a summary due to, for example, a character string reported for a numerical variable, an appropriately determined coded value will be used in the summary. The coding algorithms will be detailed in the analysis dataset specification document. The actual values as reported in the database will be presented in data listings.

6 SUBJECT DISPOSITION

The number of sites that enrolled at least 1 subject and number of subjects enrolled will be summarized by region and overall. Enrolled subjects are subjects who signed informed consent for Study ACP-103-033 and whose status in the Interactive Web Randomization System (IWRS) is “Entered Extension”, “Treatment Completed EXT” or “Discontinued Treatment EXT”. Subjects who signed informed consent for Study ACP-103-033 but failed to roll over (recorded as “Rollover Failed” in IWRS) will not be counted as enrolled subjects.

For enrolled subjects, number and percentage of subjects in the Safety Analysis Set will be summarized. A listing will be provided displaying all subjects excluded from the Safety Analysis Set (if any), and will include reason(s) for exclusion.

The number and percentage of subjects in the Safety Analysis Set who completed the study or discontinued (all discontinued and by discontinuation reason) will also be summarized. Summaries by region for the Safety Analysis Set will also be presented.

7 PROTOCOL DEVIATIONS

Protocol deviations will be reviewed periodically over the course of the study. The review process, definition of the deviation categories, and the classification of a deviation as major (significant) or minor (not significant) are detailed in the Study Deviation Rules Document.

For enrolled subjects, a summary of the number and percentage of subjects with major protocol deviations for each deviation category will be presented. A listing of protocol deviations by site and subject will be provided.

8 DEMOGRAPHICS AND OTHER BASELINE CHARACTERISTICS

Demographics and open-label Baseline characteristics will be summarized for Safety Analysis Set using descriptive statistics. Summaries by region will also be presented. Variables include age, sex, race, ethnicity, height, weight, body mass index (BMI), region, Baseline living situation category, Baseline caregiver category, Baseline NPI-C combined agitation and aggression domain score, Baseline MMSE total score, Baseline CMAI total score, Baseline ZBI total score, and concomitant selective serotonin reuptake inhibitor (SSRI) usage (yes/no).

Age (the reported age reflects a subject’s age at the open-label Baseline visit date), Baseline CMAI total score, Baseline MMSE total score, and Baseline NPI-C combined agitation and aggression domain score will be presented as both continuous and categorical variables. Age will be presented as ≤ 85 and > 85 years old. Category of Baseline CMAI will be presented as < 65 and ≥ 65 . Category of Baseline NPI-C combined agitation and aggression will be

presented as <22 and ≥ 22 . Category of Baseline MMSE will be presented as ≤ 10 , 11-20 and >20 .

Alzheimer's disease history will be summarized for Safety Analysis Set using descriptive statistics. Variables include:

- Time (year) since diagnosis of probable Alzheimer's disease
- Duration (year) of symptoms of Alzheimer's disease
- Duration (year) of symptoms of agitation/aggression

Baseline visit date will be used as the reference date for calculating the durations listed above.

A listing of living situation and caregiver information by subject and visit will also be provided.

9 MEDICAL HISTORY

Medical and surgical history data will be coded using Medical Dictionary for Regulatory activities (MedDRA) version 19.0 or newer. The subject incidence of relevant medical and surgical history data will be summarized by system organ class (SOC) and preferred term for the Safety Analysis Set. A subject will be counted only once per SOC or preferred term for the summary.

A listing of the SOC, preferred term, body system, verbatim term for the medical history condition/event, start and stop dates (when available), and an indicator for whether or not the condition is ongoing will be provided.

10 EXTENT OF EXPOSURE AND TREATMENT COMPLIANCE

Summaries of exposure and compliance to study drug will be provided for the Safety Analysis Set.

10.1 Exposure to Study Drug

Pimavanserin dose levels are expressed as free base.

10.1.1 Exposure to Open-label Pimavanserin

For each subject, the duration of exposure (in days) to open-label pimavanserin will be calculated as:

$$(date\ of\ last\ open-label\ dose) - (date\ of\ first\ open-label\ dose) + 1$$

The cumulative dose of pimavanserin will be calculated by first multiplying the number of doses taken by the dose level (in mg) for each kit returned to the site during the open-label study period and then summing the results for all kits. The average daily dose of pimavanserin (in mg) will be calculated as the cumulative dose (in mg) divided by duration of open-label exposure (in days). Duration of exposure, cumulative dose, and average daily dose for pimavanserin during open-label study period will be summarized descriptively.

Duration of open-label exposure will be summarized as both continuous and categorical variables. For categorical presentation, the number and percentage of subjects in each of the following categories will be presented: <4 weeks (1 to 27 days), 4 to <8 weeks (28 to 55 days), 8 to <12 weeks (56 to 83 days), 12 to <20 weeks (84 to 139 days), 20 to <28 weeks (140 to 195 days), 28 to <36 weeks (196 to 251 days), 36 to <44 weeks (252 to 307 days), 44 to <52 weeks (308 to 363 days) and ≥ 52 weeks (364 days or longer). Kaplan-Meier curves of duration on pimavanserin will also be presented.

In addition, summaries of whether subjects had any dose change (yes vs. no), their highest dose level (20 mg or 34 mg) and their last dose level (20 mg or 34 mg) will also be provided.

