5.8.6 Record of Dispensing

Accurate recording of all investigational drug administration for individual subjects will be made in the appropriate section of the subject's eCRF as well as in the site investigational drug dispensing and reconciliation form. Drug accountability records must be updated as subjects are enrolled and throughout the conduct of the study.

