5.8.7 Accountability

The Investigator or designee will keep current and accurate records of the investigational drug product dispensed, used, and returned for each subject to assure the health authority and Sponsor that the investigational drug is being handled appropriately. Subjects should be instructed to return all packaging, bottles, and unused medication to the Investigator at scheduled and unscheduled clinic visits when drug is dispensed and at the EOS/ET visit.

At appropriate intervals during the study, investigational drug reconciliation will be performed by the Sponsor representative who may return appropriate used and unused investigational drug and used and unused packaging to the Sponsor's designee for destruction.

At the conclusion of the study, final investigational drug reconciliation will be conducted at the site. Final investigational drug accountability documentation will be maintained at both the site and at ACADIA. Any remaining unused investigational drug and all used and unused packaging will be sent back to the Sponsor's designee for destruction. Documentation of investigational drug destruction will be recorded and maintained by both ACADIA and the Sponsor's designee.

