9.7 Safety Analyses

9.7.1 Exposure to Study Drug

For each subject, the duration of exposure to study drug will be calculated as the number of days from first dose date to last dose date inclusive. Descriptive statistics will be tabulated by treatment group. A categorical summary will also be provided using categories defined in the SAP.

In addition, the maximum dose, final dose, and mean daily dose will be determined for each subject and summarized by treatment group. For maximum dose and final dose, a categorical summary by dose level (20 mg and 34 mg) will be provided. For mean daily dose, summary statistics will be tabulated by treatment group.

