10.1.2 Total Exposure to Pimavanserin across Double-blind and Open-label Periods

For subjects who received pimavanserin in double-blind Study ACP-103-032, the total duration of exposure (in days) to pimavanserin will be calculated as the sum of the exposure durations in the double-blind and open-label periods. The cumulative dose of pimavanserin will be calculated by first multiplying the number of doses taken by the dose level (in mg) for each kit returned to the site during both the double-blind and the open-label study periods and then summing the results for all kits. The average daily dose of pimavanserin (in mg) will be calculated as the cumulative dose (in mg) divided by total duration of exposure (in days).

For subjects who received placebo in double-blind Study ACP-103-032, the total duration of exposure (in days) to pimavanserin, the cumulative dose of pimavanserin, and the average daily dose of pimavanserin across the double-blind and open-label periods will be the same as the values calculated for the open-label study period alone. Duration of exposure, cumulative dose, and average daily dose for pimavanserin across the double-blind and open-label periods will be summarized descriptively.

Duration of total exposure will be summarized as both continuous and categorical variables. For categorical presentation, the number and percentage of subjects in each of the following categories will be presented: <4 weeks (1 to 27 days), 4 to <8 weeks (28 days to 55 days), 8 to <12 weeks (56 days to 83 days), 12 to <16 weeks (84 days to 111 days), 16 to <28 weeks

(112 days to 195 days), 28 to <40 weeks (196 days to 279 days), 40 to <52 weeks (280 days to 363 days) , 52 to <64 weeks (364 days to 447 days), and ≥ 64 weeks (448 days or longer).

In addition, summaries of whether subjects had any dose change (yes vs. no), their highest dose level (20 mg or 34 mg) and their last dose level (20 mg or 34 mg) will also be provided.

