10.2 Measurement of Treatment Compliance

Study drug dosing compliance (in percentage) during the open-label study period for a subject is defined as:

$$\frac{(\text{total number of tablets actually taken})}{(\text{total number of tablets expected to be taken})} \times 100$$

With the total number of tablets actually taken calculated as:

$$(\text{the total number of tablets dispensed}) - (\text{the total number of tablets returned})$$

The number of tablets expected to be taken is calculated as:

$$(\text{the duration of exposure}) \times 2.$$

The duration is multiplied by 2 because the subject is instructed to take 2 tablets per day.

Compliance will be summarized as both continuous and categorical variables. For categorical presentation, the number and percentage of subjects in each of the following categories will be presented: <80%, 80 to 120%, and >120%.

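### SAP 10.1 counts doses only from returned kits but divides by full exposure duration, while SAP 10.2 counts every dispensed kit: read literally, an unreturned kit is 0 mg in one table and fully taken in the other

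*SAP*

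**What the plan says.** SAP 10.1.1 obtains the open-label cumulative dose by "multiplying the number of doses taken by the dose level (in mg) for each kit returned to the site during the open-label study period" and summing over kits. Average daily dose is that sum divided by open-label duration, defined as last dose date minus first dose date plus 1. SAP 10.1.2 repeats the rule "for each kit returned to the site during both the double-blind and the open-label study periods" and divides by total duration.

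SAP 10.2 counts tablets differently. Tablets actually taken are "the total number of tablets dispensed" less the total returned, with no limit to returned kits. Tablets expected are twice the duration. The reporting categories are below 80%, 80 to 120%, and above 120%.

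If the last dose date is missing, SAP 5.4.1 says "then the date of the end-of-study/early termination visit will be used in the calculation of treatment duration". Section 5.4 has no corresponding rule for a missing kit.

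The protocol makes non-return an exception. Section 5.8.7 says "Subjects should be instructed to return all packaging, bottles, and unused medication to the Investigator" and section 5.8.6 says "Accurate recording of all investigational drug administration for individual subjects will be made in the appropriate section" of the eCRF. Protocol 9.7.1 states that "the maximum dose, final dose, and mean daily dose will be determined for each subject".

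**The concern.** In 10.1 the numerator depends on which kits came back and the denominator does not. The days covered by an unreturned kit stay in the divisor while its milligrams drop out. Section 10.2 treats the same kit in the opposite way. One subject can therefore look under-dosed in the exposure table and fully or over-compliant in the compliance table, from the same drug-accountability records.

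This is a flexible-dose, 52-week safety study, and the exposure tables tell the reader how much drug lies behind the adverse-event data. The mismatch weighs most on subjects with short exposure. Protocol 4.2 lists loss to follow-up and failure to comply among the reasons for discontinuation, and in such cases bottles may plausibly not come back.

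**Working it through.** The documents give no figure for average daily dose or compliance, so there is nothing to reproduce. I applied the SAP formulas directly.

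**Inputs.** A bottle holds 60 tablets and serves 4 weeks (protocol 5.8.2). A dose is two tablets, of 10 mg or 17 mg (protocol 5.1). Visits are at Weeks 2, 4, 8 and 12, then every 8 weeks to Week 52 (protocol 3.1). **Assumptions:** one kit is one bottle; an 8-week supply is two bottles, because 8 × 7 × 2 = 112 tablets exceeds 60; nothing is recorded as returned for an unreturned bottle.

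**Formulas.** Let D be duration in days, d the days of use covered by the unreturned supply, b the tablets in it, and a the true adherence, the same throughout. For a constant 20 mg:

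- average daily dose by 10.1.1 = 20 × a × (D − d) / D; true value 20 × a
- compliance by 10.2 = [2a(D − d) + b] / (2D); true value a

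With every kit returned, d = 0 and b = 0, and both formulas give the true value.

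| Case (20 mg) | D | d | b | a | 10.1.1, mg/day | True | 10.2 compliance | True |
|---|---|---|---|---|---|---|---|---|
| Completer, one 4-week bottle | 364 | 28 | 60 | 1 | 20 × 336/364 = 18.46 | 20 | 732/728 = 100.5% | 100% |
| Completer, Baseline bottle | 364 | 14 | 60 | 1 | 20 × 350/364 = 19.23 | 20 | 760/728 = 104.4% | 100% |
| Completer, one 8-week supply | 364 | 56 | 120 | 1 | 20 × 308/364 = 16.92 | 20 | 736/728 = 101.1% | 100% |
| Stop on day 112, both Week 12 bottles | 112 | 28 | 120 | 1 | 20 × 84/112 = 15.0 | 20 | 288/224 = 128.6% | 100% |
| Same, 70% adherent | 112 | 28 | 120 | 0.7 | 20 × 58.8/112 = 10.5 | 14.0 | 237.6/224 = 106.1% | 70% |

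In the first row, 10.1.1 implies 336 × 2 = 672 tablets and 10.2 implies 732; the truth is 728. In the last row a subject who belongs below 80% is reported in the 80 to 120% category.

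**Other completer results.**

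- 34 mg from Week 2: the true average is (14 × 20 + 350 × 34)/364 = 12,180/364 = 33.46 mg/day. With one 4-week bottle unreturned it is (12,180 − 28 × 34)/364 = 30.85.
- 10.1.2, 20 mg for 84 + 364 = 448 days, one open-label 4-week bottle unreturned: 20 × 420/448 = 18.75 mg/day.
- Category error, one 4-week bottle unreturned: reported compliance reaches 80% when a = (0.8 × 728 − 60)/672 = 77.7%. Only true adherence between 77.7% and 80% is misplaced.

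**Where there is no error.** If nothing was taken from the unreturned bottle, 18.46 mg/day is correct for the first completer, but compliance still reads 100.5% against a true 672/728 = 92.3%. If the bottle was emptied, compliance is correct and the average dose is too low.

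**The case against.** The strongest case is that this is a gap in documentation and not a demonstrated bias. The SAP does not say whether an unreturned kit has a returned count of zero or a missing count; if missing, compliance might be missing and not inflated. The protocol requires drug administration to be recorded in the eCRF, so doses taken might be available from another source. Dataset and output specifications are separate documents. Return is also instructed at the early-termination visit; and if that visit does not happen, SAP 5.4.1 cannot supply a last-dose date from it. The day-112 example therefore needs a known last dose together with two bottles that never come back.

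Part of this stands. The compliance error depends on the returned count being zero, and the early-stopper figures are illustrations. The average-dose error does not depend on that reading: 10.1 explicitly limits the sum to returned kits. Nor does the SAP point to another document for unreturned kits, as it does for incomplete dates and for laboratory character values. An instruction to return bottles is not an analysis rule.

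A reader might go further and infer that average dose is understated and compliance overstated across the study, or that the safety conclusions are compromised. The documents do not support either. They give no frequency of non-return, each error has a condition under which it vanishes, and the dose and compliance calculations do not enter the TEAE or efficacy summaries. Duration, its Kaplan-Meier curves, any dose change, highest dose and last dose are not defined from kit counts.

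**Conclusion.** The point holds for subjects with an unreturned kit. For them SAP 10.1 pairs an incomplete numerator with a complete denominator, and 10.2 uses an incompatible tablet count. On a constant 20 mg with full adherence, one unreturned 4-week bottle lowers a 52-week completer's average daily dose by 28/364 = 7.7% and barely moves compliance. With two bottles unreturned and a stop on day 112, the average falls by 28/112 = 25% and compliance is wrong by 28.6 percentage points. These sizes rest on the bottle and adherence assumptions stated above. The study-level effect is unknown and would be nil if every kit is returned. The consequence is limited to descriptive tables, but the error follows from a stated rule and is cheap to remove, so the SAP should be changed.

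**What to change.** Use one count of tablets taken in 10.1.1, 10.1.2 and 10.2, over all dispensed kits: tablets dispensed minus tablets returned. For cumulative dose, multiply by tablet strength (10 or 17 mg), or equivalently halve the tablets and multiply by the dose level. Tablets times dose level would double the result: 728 × 20/364 = 40 mg/day for a fully adherent 20 mg completer.

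For unreturned kits only, cap the count at the tablets expected in that dispensing interval up to the last dose, minus those already counted from returned kits in the same interval, and not below 0. Leave returned kits uncapped so that real over-use stays visible. Both parts of the cap matter:

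- With no cap, the fully adherent day-112 subject would show 288 × 10/112 = 25.7 mg/day on a 20 mg dose.
- With no netting, a full 8-week interval with one bottle returned empty and one lost would count 60 + 60 = 120 tablets against 112 expected. Netted, the lost bottle counts 112 − 60 = 52.

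Report how many subjects have unreturned kits and show their average daily dose and compliance under both bounds, none taken and all taken up to the cap. For the fully adherent day-112 subject the bounds are 168 × 10/112 = 15.0 to 224 × 10/112 = 20.0 mg/day, and 168/224 = 75% to 100%. At 70% adherence they are 10.5 to 173.6 × 10/112 = 15.5 mg/day, and 117.6/224 = 52.5% to 173.6/224 = 77.5%. These contain the true 14.0 mg/day and 70%, and the main value stays below 80%.

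The cost is a short SAP revision and some programming. Open-label dispensing and return counts are already needed for 10.2, here by kit; 10.1.2 also needs by-kit counts from Study ACP-103-032, which 10.2 does not use. The main value is an upper bound for the unreturned kit, and the table should say so.
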